# **PROTOCOL SUMMARY**

Title:	A Prospective Open Label pilot study investigating the impact of ThermaCare on flexibility, muscle relaxation & low back pain in two different populations.			
Device(s):	
 
The devices to be used for this study include:
 
ThermaCare Lower Back HeatWraps, Pfizer Consumer Healthcare
 
ViMove wearable sensors, dorsaVi Ltd.
 
			
Study Objective:	
 
The objectives of this study are to evaluate the impact of ThermaCare HeatWraps as an intervention to:
 
Decrease pain during movement, improve muscle relaxation and increase flexibility in people with low back pain (Group 1).
 
Improve muscle relaxation and increase flexibility in people who are actively involved in sport (Group 2).
 
			
Study Design:	This research will utilize a prospective open-label investigator initiated study design. This allows the assessment of ThermaCare HeatWrap efficacy pre- and post- application, and may provide insight into the mechanisms of any observed pain relief. The nature of the ThermaCare intervention means that blinding is difficult, as there is no adequate placebo heat therapy.			
Enrolment Size:	The enrolment size will be 40 total subjects from 2 discrete population groups.  As we expect an attrition rate of 20%, we will initially recruit 50 subjects.			
Subject Population:	As per the inclusion and exclusion criteria: Group 1: 20 people with recent back pain Group 2: 20 people who regularly play sport			
Timeframe:	We expect 6-months will be required from first participant enrolment to the last participant visit. A further 3-months will be required for analysis and write-up.			
Primary Endpoints:	
 
Collection of movement and erector spinae muscle activity data in all participants.
 
A change over time in range of motion in any one plane of movement compared to pre-intervention range of motion.
 
A change over time in Flexion-Relaxation response in those subjects where abnormal EMG activity in flexion during baseline assessment is detected.
 
A change over time in maximum pain during movement score.         
 
(1-10 as recorded during the in-clinic ViMove assessment) for any one plane of movement.
 
 
 
			
Secondary Endpoints:	
 
Capture changes in low back pain levels as assessed via a Numeric Rating Scale (NRS-Pain).
 
Capture self-reported changes in functional status pre- and post-ThermaCare application as measured by the Oswestry Disability Index (ODI) and Roland Morris Disability Questionnaire (RMDQ) if subjects scored >3 on the NRS.
 
Capture impression of change from subjects post ThermaCare application using the Patient Global Impression of Change Scale (PGIC).
 
Observe changes in activity levels as collected by ViMove monitoring.
 
Correlation of Low Back Pain Classifier (LBPC) Score to ViMove Scores for flexion and extension.
 
			

#### **Inclusion Criteria:**

#### Inclusion criteria for recent low back pain patients:

- 1. Adults between the age of 21-54 inclusive, male and female.
- 2. Low back pain is the primary source of pain over the last 3 weeks.
- 3. Have experienced and/or received treatment for muscle related low back pain with an average score of at least 3/10 on a 10-point Numeric Rating scale over the past 3 weeks.
- 4. Must be able to communicate fluently in English.
- 5. Must provide written informed consent.
- 6. Must agree to confidentiality.

### Inclusion criteria for people who are active in sports:

- 1. Adults between the age of 21-54 inclusive, male and female.
- 2. Participate in 30 min of moderate to high intensity exercise 3 times per week, as defined by the Borg Rating of Perceived Exertion scale.
- 3. Must be able to communicate fluently in English.
- 4. Must provide written informed consent.
- 5. Must agree to confidentiality.

#### **Exclusion Criteria:**

- 1. The subject is pregnant.
- 2. The subject has a severe hearing impairment or an inability to follow verbal instructions in English.
- 3. The subject is cognitively impaired.
- 4. Known allergic skin reaction to tapes and plasters.
- 5. Co-morbidities of neoplasm, infection, fracture, inflammatory or metabolic disorder that has potential to affect the lumbo-pelvic region.
- 6. Preceding chronic myelopathy, specific neurological disease or neurological changes.
- 7. Person who is currently enrolled in another investigational drug or device study.
- 8. Any past or current heart or blood-circulation related disorders.
- 9. The subject is contraindicated for this study for any other reason.

### 1: INTRODUCTION

Low back pain commonly occurs in the general population, making it an important target for intervention. ThermaCare HeatWraps may prevent and relieve pain in regions such as the low back through continuous, low-level, direct heat therapy. The objective of this Investigator Initiated study is to evaluate the effectiveness of ThermaCare HeatWraps in improving flexibility and low back muscle relaxation, and in participants experiencing pain, reducing pain during movement. This study is an intervention trial on two discrete subject samples; (1) people with recent back pain, and (2) people who regularly play sport. ViMove wearable sensors provide precise objective measurements of low back muscle activity and movement in real time and can capture a patient's reporting of pain during movement. Outcomes will be assessed through standard ViMove protocols in conjunction with multiple validated measures of pain, perception of change, and function.

## 2: BACKGROUND

Low Back Pain (LBP) is common in the general population with a 12-month point prevalence of 12% and 1-month prevalence of 23% [1]. Nonspecific LBP, the most common presentation, is defined as pain of unclear pathology below the costal margin and above the inferior gluteal folds [2-5]. Although the prognosis for LBP appears to be favorable, rates of chronicity are high [6] with previous LBP being a strong risk factor for ongoing complaint or relapse [7]. This makes LBP one of the leading causes of years lived with disability in developed countries [8], resulting in direct and indirect costs of \$84.1 to \$624.8 billion in the United States [9]. As such, addressing LBP effectively is necessary to minimize the associated physical and financial burden [10].

There are numerous proposed methods to treat LBP. Effective interventions include spinal manipulation, and medications such as painkillers [11, 12]. However, these interventions can be invasive and are associated with extensive time requirements, high costs, and adverse side effects [13, 14]. Thus, non-invasive and easy-to-administer treatments such as heat therapy may be preferred, although their effectiveness is not as consistent [12, 15]. One such heat therapy is in the use of ThermaCare HeatWraps (Pfizer Consumer Healthcare, Richmond, VA). ThermaCare is a brand of non-invasive disposable heat wraps which provide the wearer with continuous low-level direct heat therapy for approximately 8 hours. ThermaCare HeatWraps are customized for specific parts of the body, including the low back. Clinical trials have demonstrated the efficacy of this intervention in the early treatment and prevention of Delayed Onset Muscle Soreness (DOMS) [5, 16]. Moreover, ThermaCare has been shown to be effective in the prevention of post-exercise pain and muscle soreness [16, 17]. Compared with the pain relievers ibuprofen and acetaminophen, ThermaCare provided more effective pain relief, and significantly improved flexibility and disability [18].

However, these studies are limited in their assessment of pain and disability. Pain was often measured using Likert-scale questionnaires, as pain is an inherently subjective experience despite being physiologically determined [19]. Disability was assessed using more comprehensive questionnaires, but was not compared with objective measures [20]. This is despite objective measures of movement being correlated with disability scores [21]. A Cochrane review assessing the efficacy of heat therapies such as ThermaCare, indicated that there is only moderate support from current research, as effects

are transient and relatively small [22]. However, these reviewed studies may be limited due to their qualitative and subjective measurement of pain and disability [23]. A systematic review and meta-analysis further indicated that current heat therapy research is of "very-poor-quality" [24]. As such, validated, objective and quantitative data into muscle activity and movement is required, to provide insight into subjectively reported changes in pain and disability.

Objective assessment of the association between pain and movement, and capturing a detailed view of the person's movement, postures and activity levels is now possible due to the development of portable biofeedback sensors such as ViMove (dorsaVi Ltd). ViMove is wearable sensor technology, designed to precisely measure range of movement and static postures [25-27]. The device also measures low back muscle activity in real time through additional electromyography sensors. ViMove assessment of low back range of movement and posture has been shown to be highly correlated with 3D kinematic measurement [26]. Normative low back range of movement values have also been determined and are available for the adult population (normative data has FDA clearance, available upon request). The device also demonstrates high intra- and inter-rater reliability as a low back measurement tool [27]. Objective information and feedback is provided to the practitioner as a report evaluating a patient's movement and function/activity pre- and post- low back pain intervention. The wearable and portable nature of the device allows monitoring in non-clinical environments for up to 24 hours (i.e. during normal daily activities). ViMove devices have TGA approval and FDA 510K clearance for use in Australia and the USA respectively.

By utilizing ViMove, this study will objectively assess muscle activity and movement, prior to, during, and following the use of ThermaCare HeatWraps. This study will include 2 discrete population samples; (1) people with recent back pain, and (2) people who regularly play sport. As such, it will evaluate the efficacy of ThermaCare in these respective samples. Previous research has primarily assessed ThermaCare as an intervention in the USA, with the efficacy of ThermaCare not being examined in Australian samples. However, epidemiological studies indicate comparable prevalence of low back pain between the two countries [28, 29].

# 3: AIMS, HYPOTHESES, AND OBJECTIVES

#### **3.1** Aims

The aims of this study are to evaluate the efficacy of ThermaCare HeatWraps:

- 1. As an intervention for people with low back pain.
- 2. As an intervention for people who are actively involved in sport.

# 3.2 Hypotheses

The Hypotheses for each aim are as follows:

- 1. ThermaCare HeatWraps are an effective intervention for people with low back pain as it:
  - a. Decreases pain during movement.
  - b. Improves muscle relaxation.
  - c. Increases flexibility (range of movement).
- 2. ThermaCare HeatWraps are an effective intervention for people actively involved in sport as it:
  - a. Improves muscle relaxation.
  - b. Increases flexibility.
  - c. Delays or reduces the incidence of pain as defined by an increase in existing pain or the occurrence of new pain.

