### 11.2 Statistical Methods

An initial descriptive analysis will be completed on the baseline measures of movement to determine mean scores, ranges and standard deviations of each sample group. This analysis will be repeated at later time points. Wilcoxon Signed Ranked Tests will be completed to determine if participant movement significantly changes following an intervention: One each for Baseline and Intervention. A repeated measures ANOVA will then be completed on all post trial data for the 2 separate groups to determine movement changes in the post-trial period.

Bivariate correlational analyses through the Pearson product-moment coefficient, will be undertaken to determine if there is a relationship between movement and "pain on movement" using data collected at each time point. This potential relationship will be mapped to assess any temporal influences.

Similarly, correlational analyses will be conducted to determine if there is a relationship between daily activity and ODI scores, using data collected at each of the four total time points. This potential relationship will also be mapped over time to determine if there are any temporal effects following initial treatment.

All findings with a p-value < 0.05 will be deemed significant.

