### 13: STUDY OUTCOMES AND SIGNIFICANCE

# **13.1 Primary Endpoints**

- 1. Collection of movement and erector spinae muscle activity data in all participants.
- 2. Change over time in range of motion (ROM) in any one plane of movement compared to preintervention ROM.
- 3. A change over time in Flexion-Relaxation response in those subjects where abnormal EMG activity in flexion during baseline assessment is detected.
- 4. A change over time in maximum pain during movement score (1-10 as recorded during the inclinic ViMove assessment) for any one plane of movement.

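### Three unranked primary outcome changes feed one effectiveness claim per population, and nothing says whether all or any of them must be met

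*Combined protocol and SAP*

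**What the plan says.** Section 3.2 states one effectiveness claim per population. For Group 1 it is "ThermaCare HeatWraps are an effective intervention for people with low back pain as it", followed by (a) less pain during movement, (b) better muscle relaxation and (c) greater flexibility. For Group 2 it is "ThermaCare HeatWraps are an effective intervention for people actively involved in sport as it", followed by (a) relaxation, (b) flexibility and (c) later or less frequent new or worsened pain. Neither list has an 'and', an 'or' or a success rule.

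Section 13.1 and the matching list in the Protocol Summary name four primary endpoints in no order of importance:

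1. The first is a feasibility item with nothing to test: "Collection of movement and erector spinae muscle activity data in all participants".
2. The second concerns flexibility and leaves the plane open: "Change over time in range of motion (ROM) in any one plane of movement compared to preintervention ROM".
3. The third concerns muscle relaxation and applies only to a subset whose size is not given: "A change over time in Flexion-Relaxation response in those subjects where abnormal EMG activity in flexion during baseline assessment is detected".
4. The fourth concerns pain and again leaves the plane open: "A change over time in maximum pain during movement score".

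Section 11.2 assigns a test of change only to movement: "Wilcoxon Signed Ranked Tests will be completed to determine if participant movement significantly changes following an intervention". It closes with a rule for everything: "All findings with a p-value < 0.05 will be deemed significant".

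On purpose, the title calls the study a pilot, and sections 8.2 and 11.1 describe feasibility work to guide a randomised trial. Yet the last paragraph of section 2, section 3.1 and section 4 all speak of evaluating efficacy.

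**The concern.** The plan has one conclusion per population, several primary results that bear on it, and no stated route from the results to the conclusion. Suppose that in Group 1 range of motion gives p = 0.03 while flexion-relaxation and pain on movement each give p = 0.4. A reader who takes the list in 3.2 as conjunctive says effectiveness was not shown. A reader who applies the 0.05 rule result by result can say that it was. The text excludes neither, and the choice could be made after the results are known, in a study whose treatment is open-label.

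The two readings also have very different error rates. Requiring every component keeps the error of the claim at or below 5%. Letting any one component suffice does not.

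This is separate from the choice of plane within endpoints 2 and 4. The gap would remain if one plane and one test were fixed for each endpoint.

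**Working it through.** **The plan's own figure.** The plan states no power and no overall error rate. Its one reproducible design figure is recruitment: 40 / (1 − 0.20) = 50, which matches sections 6 and 11.1.

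**Inputs**
- Threshold: 0.05 per finding (11.2), with no split.
- Testable primary changes: three (13.1, endpoints 2 to 4). Endpoint 1 is data collection and is not counted.
- Sidedness: not stated; assumed two-sided.
- Tests: 11.2 names a test of change only for movement. One 0.05 test for each of the other two is an assumption, resting on the all-findings sentence.
- Correlation between the test statistics: not given; a common value from 0 to 0.8 is shown.

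**Mapping to the claims.** In Group 1, hypotheses 1a, 1b and 1c correspond to endpoints 4, 3 and 2, so m = 3. In Group 2, 2a and 2b correspond to endpoints 3 and 2. Hypothesis 2c concerns the incidence of new or increased pain, whereas endpoint 4 is a change in a maximum pain score, so 2c has no matching primary endpoint. On that mapping m = 2.

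**Any one suffices.** For independent tests the chance of at least one false positive is 1 − 0.95^m:
- m = 3: 1 − 0.857375 = 0.1426
- m = 2: 1 − 0.9025 = 0.0975

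For equally correlated normal test statistics, by numerical integration:

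| Correlation | Group 1, m = 3 | Ratio to 0.05 | Group 2, m = 2 | Ratio to 0.05 |
|---|---|---|---|---|
| 0 | 14.3% | 2.85 | 9.75% | 1.95 |
| 0.5 | 12.5% | 2.51 | 9.1% | 1.82 |
| 0.7 | 10.9% | 2.18 | 8.3% | 1.67 |
| 0.8 | 9.8% | 1.96 | 7.8% | 1.56 |

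In Group 1 the figure passes below 10% at a correlation of about 0.78 (10.06% at 0.78, 9.95% at 0.79).

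**All must be met.** If no component has an effect and the tests are independent, the chance of a false claim is 0.05³ = 0.000125. It is about 0.3% at correlation 0.5. If some components do have an effect and one does not, the claim still needs that one to pass at 0.05, so the error cannot exceed 5%.

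**Adjusting and requiring all at once.** Take three p-values of 0.04. Each is below 0.05, so an all-must-pass rule is met. Holm compares the smallest with 0.05/3 = 0.0167, and since 0.04 > 0.0167 it rejects none. Combining the two rules is therefore stricter than either purpose needs.

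**The case against.** The strongest reply is that the plan never says one significant result makes the wrap effective. Section 11.2 labels findings significant; it does not declare success. The wording of 3.2 reads most naturally as all components, or as component by component. Section 3.3 asks what the wraps affect, and 13.3 promises only information about changes. In a pilot with 20 per group and no power statement, formal family-wise control is partly a matter of taste. All of this stands, and it is why the 10% to 14% is conditional on the any-one reading. It does not close the gap: no sentence commits the analysis to the all-components reading, and the efficacy language together with a blanket significance rule leaves the other reading open.

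Three stronger inferences are tempting and are not supported:
- *That the error always more than doubles.* In Group 1 this fails above a correlation of about 0.78, and the documents give no correlation. In Group 2 with two matching endpoints it fails under independence and under any positive correlation.
- *That each group contributes three tests, six in all.* Hypothesis 2c matches no primary endpoint, and the Study Objective in the summary names only relaxation and flexibility for Group 2. Objective 2 in section 3.3 does add perceived pain. If endpoint 4 were meant to serve Group 2's claim, the Group 1 column would apply there too, but the plan does not say so. The two populations are also separate questions, so a pooled figure answers neither.
- *That three full 0.05 tests are specified.* Only movement has a named test of change. Flexion-relaxation is limited to subjects with abnormal baseline EMG, and the size of that subset is not given. If a signed-rank test were used with five subjects, the smallest exact two-sided p would be 2/2^5 = 0.0625, and that endpoint could add no error at all.

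**Conclusion.** The point holds as a missing decision rule: three unranked testable primary changes, one effectiveness claim per population, and a blanket 0.05 rule with nothing connecting them. If any one result may carry the claim, the false-positive chance is about 10% to 14% in Group 1 and about 8% to 10% in Group 2.

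These figures assume one two-sided 0.05 test per endpoint, a common correlation between 0.8 and 0, and, for Group 2, that only relaxation and flexibility map to primary endpoints. They leave out the choice of plane within endpoints 2 and 4. If all components are required there is no inflation.

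The feasibility purpose lowers the stakes, but the plan still hypothesises effectiveness and tests for significance. The rule should be settled before the data are analysed, because it decides what the study may conclude.

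**What to change.** **Preferred, and consistent with the title and with sections 8.2 and 11.1.** In 3.2, 11.2, 13.1 and the Protocol Summary:
- label the changes in range of motion, flexion-relaxation and maximum pain on movement as exploratory;
- report each one separately by population, as an estimate with a 95% CI;
- replace the blanket p < 0.05 sentence in 11.2;
- remove effectiveness as a conclusion that this study can reach.

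**If an effectiveness claim is kept.** Name one test per component, say which outcome tests hypothesis 2c, and state one of the following in advance, but not both together:
- all components must reach 0.05 in the hypothesised direction, with no alpha split; or
- claims are made component by component, with Holm across the components within each population (for three: 0.0167, then 0.025, then 0.05).

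**Cost.** The changes are to wording only, with no extra subjects, visits or data. The preferred option gives up an unqualified significance claim from about 20 subjects per group. The Holm option sets a stricter threshold for the smallest p-value; the power lost cannot be stated, because the plan gives no effect size or standard deviation.

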# 3.3 Objectives

The objectives of this study are to determine if ThermaCare HeatWraps:

- 1. Affect muscle relaxation, perceived pain, and flexibility in people with low back pain.
- 2. Affect muscle relaxation, perceived pain, and flexibility in people who are actively involved in sport.
- 3. Result in changes in subjective measures of pain and disability following 8-hours of usage.
- 4. Induce changes in movement and surface muscle activity, by collecting and assessing objective movement and EMG data pre- and post- intervention.

### 4: STUDY DESIGN

This investigator-initiated study will utilize a prospective open-label study design. This allows the assessment of ThermaCare HeatWrap efficacy pre- and post- intervention, and may provide insight into the mechanisms of any observed pain relief. The nature of the ThermaCare intervention means that blinding is difficult, as there is no adequate placebo heat therapy.

#### 1. In clinic assessments:

- a. Obtainment of demographic data and brief medical history.
- b. ViMove Assessment comprised of:
  - i. Assessment of Range of Movement (ROM) Flexion, Extension, Lateral Flexion, and rotation, standing and sitting positions, walking (40m speed test), sit-to-stand test (number of repetitions in 30 seconds and movement pattern, lift and carry task and squatting task).
  - ii. Simultaneous collection of muscle activity data using ViMove EMG sensors.
- c. Questionnaires:
  - i. Oswestry Disability Index (ODI)
  - ii. Roland Morris Disability Questionnaire
  - iii. Low Back Pain Classifier
  - iv. Numeric Scale for Pain (NRS-Pain)
  - v. Patient's Global Impression of Change Scale (PGIC)

